**PHYSIOLOGICAL RESPONSE TO A TRAINING AND DETRAINING PERIOD
IN VASCULAR PARAMETERS OF CARDIOMETABOLIC RISK FACTORS
SUBJECTS: OPTIMIZING POST-EXERCISE STRATEGIES TO MAINTAIN
HEALTH BENEFITS IN CHILEAN ADULTS**

Date: June 20th, 2022

Study documents

Scientific background: Atherosclerosis is a chronic disease characterized by the accumulation of lipid cells in the inner layer of artery walls, often as a result of oxidative damage to low-density lipoprotein (LDL-c) ¹. LDL-c accumulation can lead to inflammation in the major arteries (*e.g.*, carotid and brachial arteries), which usually progress to fibroatheromas ². However, before the development of atherosclerosis, endothelial dysfunction (EDys) is a phenotypic (*i.e.*, intermediate pathology condition) vascular alteration of the endothelium, characterized by a pro-thrombotic and pro-inflammatory state as result of imbalance between the actions of vasodilators and vasoconstrictors, modifying thus both ‘function’ and ‘structure’ of the vasculature ³. Given that traditional methods for detecting EDys are highly invasive, expensive, and time-consuming (*e.g.*, coronary epicardial vasoreactivity, venous occlusion plethysmography), non-invasive methods based on ultrasound imaging have been rapidly implemented in clinical management ^{4,5}.

EDys is often associated with several health conditions including arterial hypertension (HTN), obesity, coronary artery disease, chronic heart failure, peripheral artery disease, diabetes, metabolic syndrome, non-alcoholic fatty liver disease, and chronic renal failure ⁶. In Chile, 26.9% of adults are HTN, and this prevalence is highly superior in elderlies ⁷, therefore, it is estimated that an important number of adults and older adults will develop EDys, that will progress to atherosclerosis, or to an atheromatous plaque that in turn will increase the risk of stroke. From ‘functional’ parameters, the percentage of flow-mediated dilation (FMD) has been a more suitable a non-invasive and strong marker of vascular health in adults, where low values of FMD (*i.e.*, <6.5%) denotes an impaired vascular function associated with cardiometabolic risk ^{4,8}. To both ‘functional’ and ‘structural’ modifications, the pulse wave velocity of the brachial artery (PWVba) is a recognized marker of arterial stiffness in adults, where >10 cm/s indicates

high cardiovascular risk ⁹, and on the other hand, carotid-intima media thickness (cIMT) is a well established marker of structural vascular health ¹⁰.

It is well known in physical inactivity (*i.e.*, does not follow international physical activity guidelines of 300 min/week of low-moderate PA or at least 150 min/week of vigorous intensity [11,12]) is in higher prevalence in sedentary, obese, higher blood pressure, dyslipidaemias or suffering from metabolic syndrome, that there is a negative effect on both functional and structural vascular parameters such as FMD, PWVba, and cIMT ⁴. Relevant American and Latin American expert panels have recommended performing moderate intensity continuous training (MICT) for 30-60 minutes per session most days of the week in subjects with elevated blood pressure or HTN patients ¹¹. In this sense, other experts have also confirmed that MICT is crucial for preventing and treating hypertension ^{12,13}, and recent evidence highlight the time-efficient of high-intensity interval training ^{14,15}, and resistance training for improving EDys similarly ¹⁶.

However, before starting any exercise training program in clinical populations such as those with elevated blood pressure or HTN, it will necessary to know the baseline of the cardiovascular response to the physical effort through of a progressive exercise volitional test, such as a cycling test [16,17]. A progressive volitional cycling test like the Astrand test provides useful information about the cycling power output (PO) in watts, which increases at different levels (*e.g.*, in women PO increases by 25 watts per level and in men it increases to 50 watts), while heart rate should also increase progressively at each level [17,18]. Interestingly, the theoretically predicted heart rate maximum ($HR_{\text{predicted}}$) using the well-known formula (*i.e.*, 220-age) is often overestimated or underestimated in physically inactive individuals [19]. Additionally, the use of heart rate maximum (HR_{max}) is poorly reported in physically inactive hypertensive populations that are generally unable to maintain a steady state at maximal intensity. From here, the heart rate peak

(HR_{peak}) is a useful marker of cardio-vascular condition and it has been widely used for exercise prescription in the future. The aim of this study was to assess the relationship between EDys markers (FMD, PWVba, and cIMT) and heart rate during a progressive volitional cycling test in adults with hypertension. A secondary aim was to characterize cardiovascular, anthropometric, and body composition outcomes in normotensive, elevated blood pressure, and hypertension patients.

This study will follow the CONSORT guidelines for randomised trials, will be developed in accordance with the Declaration of Helsinki (2013), and has been approved by the BIOETHICAL COMMITTEE OF UNIVERSIDAD ANDRES BELLO (Approval 026/2022 of September 22th). **Design:** An experimental clinical randomized study. **Methods:** This study is an experimental randomized controlled clinical trial in which (n=75) adults (men and women) were invited to participate in an exercise training intervention and were assigned to one of three groups based on their blood pressure levels: arterial hypertension (HTN), elevated blood pressure (Ele), or to a normotensive control group (CG). The study took place in Concepción, Chile between September 2022 and January of 2023. We used G*Power 3.1.9.7 statistical sample size software calculator, with an *alpha* error probability of $p < 0.05$, and with 95% confidence interval (CI) for 3 groups (expecting medium to-large effect size) for obtain the sample size. Thus, a minimum of ten subjects per group would give a statistical power of $\geq 90\%$].

The eligibility criteria for this study were: i) HTN, elevated blood pressure (controlled and on updated pharmacotherapy), or healthy normotensive; ii) normal weight, overweight, or obese (as determined by body mass index [BMI]); iii) normal or hyperglycaemic (T2DM, controlled and on updated pharmacotherapy); iv) living in urban areas of the city of Concepción; and v) demonstrated ability to adhere to all measurements and stages of the study. Exclusion criteria included: i) abnormal ECG; ii) uncontrolled


Statistical Analysis Plan (SAP): Data are presented as mean and (\pm) standard deviation (SD). The normality assumption for all variables was tested using the Shapiro–Wilk test. Wilcoxon’s rank sum test was used for not normally distributed variables. A one-way ANOVA will be performed to test differences between groups and a *post hoc* [Sidack’s] test after ANOVA for group comparisons (*i.e.*, HTN x Ele x CG). Additionally, we will report a trend analyses [*ptrend*] to test potential (linear) tendency to increase or decrease a particular outcome through these categories of different blood pressure. Finally, using the first three steps of the progressive volitional cycling Astrand test (*i.e.*, 25/50, 50/100, and 75/150 watt) we will apply a linear regression among EDys outcomes FMD, PWVba, cIMT to be associated with the heart rate (beats/min) in these three steps, and the R^2 will be tested as predictive capacity from this heart rate for EDys outcomes. These analyses will be performed using Graph Pad Prism 8.0 software (Graph Pad Software, San Diego, CA, USA). The alpha level was set at $p < 0.05$ for statistical significance.

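### The regression of vascular markers on step heart rate has no age term, so its R² cannot show that heart rate predicts anything beyond age

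*Combined protocol and SAP*

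**What the plan says.** The first aim, at the end of the scientific background, is to relate the three vascular markers to heart rate during a progressive cycling test in adults with hypertension. The SAP serves that aim with one sentence: "we will apply a linear regression among EDys outcomes FMD, PWVba, cIMT", the markers being "to be associated with the heart rate (beats/min) in these three steps". The steps are absolute workloads, "25/50, 50/100, and 75/150 watt", the lower figure for women and the higher for men. R² is then to be "tested as predictive capacity from this heart rate for EDys outcomes".

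The SAP names no covariate for this regression. It does not say whether the model is run in the hypertensive group alone (n=18) or in all three groups together (18 + 22 + 21 = 61). The eligibility list in the Methods covers blood pressure, weight, glycaemia, residence and adherence, and gives no age range for the adults enrolled.

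The background reports that hypertension is more prevalent in older people and lists hypertension among the conditions associated with endothelial dysfunction. It brings age into heart rate only through the 220-minus-age prediction of the maximum, which it says "is often overestimated or underestimated in physically inactive individuals".

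**The concern.** Calling R² predictive capacity invites the reading that heart rate at a light workload tells the clinician something about the endothelium. For that to be useful, heart rate must carry information that is not already in the participant's age. The background gives age a plausible route to the outcome side, and the design does nothing to limit the spread of age. If age also moves heart rate at these workloads, a model with heart rate alone gives a slope and an R² made up in part, or wholly, of age. Nothing in the planned output would let a reader tell the two apart. What is at stake is the interpretation of the result that answers the first aim. The comparisons between blood-pressure groups are a separate matter.

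**Working it through.** **Is there a plan figure to reproduce?** No. The sample-size statement (ten per group, power of at least 90%) is framed for three groups and gives neither a numerical effect size nor a test family. It says nothing about this regression, and the point does not rest on it.

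**Inputs from the documents.** Predictor: raw beats/min. Covariates: none. Sample size: 61 pooled or 18 in the hypertensive group. Alpha: 0.05, with two sides assumed because the SAP does not say.

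**Inputs assumed.** Let a be the correlation of age with step heart rate and b the correlation of age with the marker. The documents give neither. The range used is |a| = 0.2 to 0.5 and |b| = 0.4 to 0.6, and a = 0 is shown as well.

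**Step 1: crude correlation produced by age alone.** If heart rate and marker have no link except age, their crude correlation is r = a × b, and the population R² is r².

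- Low end: 0.2 × 0.4 = 0.08, R² = 0.0064.
- High end: 0.5 × 0.6 = 0.30, R² = 0.09.

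**Step 2: how often the crude slope test rejects.** Test statistic: t = r√(n − 2)/√(1 − r²) on n − 2 degrees of freedom, in 20,000 simulated trials per cell with normal variables.

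| a × b | r | Population R² | Rejects, n=61 | Rejects, n=18 |
|---|---|---|---|---|
| 0 × 0.5 | 0 | 0 | about 5% | about 5% |
| 0.2 × 0.4 | 0.08 | 0.0064 | about 10% | about 6% |
| 0.3 × 0.4 | 0.12 | 0.0144 | 15% | about 7.5% |
| 0.3 × 0.5 | 0.15 | 0.0225 | 21% | 9% |
| 0.4 × 0.5 | 0.20 | 0.04 | about 34% | 12% |
| 0.5 × 0.6 | 0.30 | 0.09 | 66% | 23% |

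A noncentral-F calculation agrees closely: 9.5% and 67.6% at the two ends for n=61, and 6.2% and 24.1% for n=18.

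**Step 3: what a significant crude R² looks like.** The smallest R² reaching p < 0.05 is t²/(t² + n − 2) at the critical t. This is 0.064 at n=61 and 0.219 at n=18. At n=18, an age-driven R² that does reach significance will therefore look large.

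**Step 4: does an age term remove it?** With age in the model, the test of heart rate on n − 3 degrees of freedom rejected in about 5% of trials in every row, at both sample sizes.

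**Step 5: cost of the age term.** At n=61, power to detect a partial correlation of 0.4 is 0.918 with or without the extra term.

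**The case against.** The strongest reply is that the plan asks only about a relationship and about prediction. It claims no independent or causal effect. If heart rate and marker both move with age, their crude correlation really is non-zero and rejecting a zero slope is correct. That stands. A reader might infer from the table that the plan's false-positive rate is 10–66% instead of 5%. The documents do not support that, because the crude test keeps its nominal level for the crude question. The figures say how often an association due wholly to age would be credited to heart rate. The reply does not remove the need for the partial R², which answers whether heart rate adds anything to age; the crude R² cannot.

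A second tempting inference is that the SAP contradicts its own rationale by leaving out HRpeak. The background says that HRpeak "is a useful marker of cardio-vascular condition and it has been widely used for exercise prescription in the future". That passage recommends HRpeak for prescribing exercise and does not propose it as a predictor of the three markers. The aim speaks only of heart rate during the test, which step heart rate answers. The background also says that inactive hypertensive people generally cannot hold a steady state at maximal intensity, which if anything favours submaximal steps. Expressing heart rate as a percentage of HRpeak could also bring age in. In a simulation with step heart rate independent of age (assumed mean 120, SD 15; age SD 8–12; HRpeak = 220 − age plus noise of SD 5–15), raw heart rate correlated 0.00 with age but the percentage correlated 0.29–0.48.

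Third, the size is assumed. No passage says that age is related to heart rate at 25–150 W, and the 220-minus-age formula concerns the maximum. The upper end of the range also needs a pooled analysis that the SAP does not state, while the aim names adults with hypertension. Age and exercise capacity could partly offset each other. All of this stands. It limits what can be said about magnitude, not the fact that the planned output cannot separate heart rate from age.

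Finally, age is not the only omission. Men cycle at twice the women's load and no sex term is named; pharmacotherapy is likewise unaddressed. An age term does not deal with either.

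**Conclusion.** The point holds as one of interpretation. As written, the regression can describe the crude association between step heart rate and each marker, but it cannot support a statement that heart rate predicts endothelial dysfunction beyond what age already tells. How much this matters cannot be derived from the documents: it ranges from nothing, if age is unrelated to step heart rate, to misattribution in about two-thirds of pooled analyses at the top of the assumed range. If the model is confined to the hypertensive group, the range is 6–23%. The conclusion rests on a route from age to the markers that the background makes plausible without quantifying it, and on the lack of any age limit or age term. The change is worth making because it settles the question at almost no cost.

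**What to change.** In the SAP, keep the crude regression and its R² as description. Add age in years as a covariate in each heart rate–marker regression. Report the partial R² of heart rate over the model with age alone, next to the crude R², and make the partial R² the basis for any statement on predictive capacity. If a sensitivity analysis with heart rate as a percentage of the participant's own HRpeak is added, it should keep the age term, because HRpeak itself depends on age.

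The cost is a few lines of SAP wording and one degree of freedom per model. It assumes that age was recorded, which would be usual but which the documents do not list.
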